CLINICAL PROTOCOL

409 **Aim 1.1** the superiority of the PF over Sensor-augmented mode (SAM) in controlling GV. PF is a
410 system designed to provide patients with *actionable information* about glucose control in general
411 and GV in particular (e.g. estimated HbA1c (eA1c), risk of hypoglycemia, and activity level);

412 **Aim 1.2** the superiority of the DSS over SAM in controlling GV. DSS is a CGM-based system that
413 includes PF and further assists with treatment recommendations for common metabolic
414 challenges;

415 **Aim 1.3** the overall non-inferiority of DSS over PF intervention to control GV and superiority of
416 DSS to maintain tight glycemic control over time (lower variations of GV in time).

417 **Aim 2 (personalization of treatment policy)** We hypothesize that the participants in this study
418 will have technology intervention preferences (e.g. PF or DSS) that can be predicted by key
419 psychosocial and behavioral parameters and are prognostic of the level of GV control achievable
420 by the intervention. We will:

421 **Aim 2.1** confirm that technology acceptance and trust are predictive of the level of GV control
422 achieved during the study (see Aim 1), regardless of the type of DSS system in use. We
423 hypothesize that technology acceptance will correlate negatively with GV: i.e. higher technology
424 acceptance leads to lower GV;

425 **Aim 2.2** explore the impact of technology expectations and experience on the performance of
426 each type of technology intervention (SAM, PF, DSS). For example, higher expectation will
427 negatively correlate with GV for the SAM treatment, but not the DSS treatment.

428 **Aim 2.3** assess the correlation between relevant psycho-behavioral traits with the performance
429 of PF vs DSS, identifying potential pathways to the corresponding optimal technology-based
430 treatment policies.

431 **1.3. Outcomes**

432 **1.3.1. Glycemic outcomes**

433 The primary outcome of this study will be Glucose Variability (GV) as measured by CGM-based
434 Coefficient of Variation (CV), as recommended by the International Consensus on Use of
435 Continuous Glucose Monitoring. To further characterize glucose control, we will compute other
436 CGM Consensus outcomes as well:

437 Average

438 Percent in different ranges:

439 ○ <50 mg/dL

440 ○ <54 mg/dL

[figure not shown]
CLINICAL PROTOCOL

- 441 ○ <60 mg/dL
- 442 ○ <70 mg/dL
- 443 ○ ≤70-≤180 mg/dL
- 444 ○ >180 mg/dL
- 445 ○ >250 mg/dL
- 446 ○ >300 mg/dL

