476 experience. This will examine relevant core constructs of trust, acceptance, satisfaction,
477 confidence as well as fear, worries, distress and burden. Validated and reliable measures will be
478 used to explore psycho-behavioral characteristics and outcomes in addition to specifically
479 adapted measures for SAM and DSS technologies to capture holistic, disease-specific and
480 technology-specific data. These questionnaires will evaluate how specific constructs are
481 predictive of successful glycemic outcomes associated with DSS. These questionnaires will enable
482 us to assess important non-glycemic treatment outcomes that are meaningful to patients
483 including those affecting Quality of Life (QOL) (e.g. fear of hypoglycemia and diabetes distress).
484 To those ends, participants will complete a battery of questionnaires related to diabetes
485 management, treatment satisfaction and QOL at baseline (before system use) and after each
486 treatment modality.

487 **1.3.5. Ecological Momentary Assessment Data Collection**

488 Participants will be trained on the EMA surveys and requirements. During each treatment
489 condition, over the course of 2-3 days every two weeks, the participant will be asked to complete
490 a "Daily Diary" with 3-5 entries of 3-4 questions each day, for a minimum total of 48 entries per
491 participant during each Phase. The DiAs phone will display a text message containing a link to the
492 survey. Surveys will be triggered at fixed times, including a morning survey ~1h after waking up
493 and an end-of-the-day survey around 8-9 PM. Participants will be able to delay (up to 30 min) or
494 skip (up to 2 per day excluding at wake up) surveys for their convenience. Participants will
495 respond to questions on a 5-point Likert scale (0=Not at All, 4=Extremely). The first Diary for each
496 day will contain two additional items for rating sleep quantity/quality. The Daily Diary questions
497 are intended to assess agreement, trust, treatment satisfaction, diabetes burden, self-efficacy,
498 mood valence, energy level, physical well-being, and concerns about hypo- and hyperglycemia.
499 The first Diary for each day will contain two additional items for rating sleep quantity/quality.

CLINICAL PROTOCOL

500 **1.3.6. Mapping of Psycho-behavioral Characteristics to DSS Preferences and Performance**

501 Baseline assessments of psycho-behavioral traits will be introduced as covariates in the general

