942 **6.7.1. Phase 3 EMA Surveys**

943 Over the course of 2-3 days every two weeks of Phase 3, the participant will be asked to complete
944 a “Daily Diary” with 3-5 entries of 3-4 questions each day, for a minimum total of 48 entries per
945 participant during each Phase.

946 **6.7.2. Post-Phase 3 Questionnaires Week 7**

947 Participants randomized to escalation will be sent the following questionnaires on week 7 (day
948 42 of Phase 1) and will be asked to complete them within 1 week:

- 949 • Technology Acceptance (burdens subscale only)
- 950 • Pittsburgh Sleep Quality Index.
- 951 • T1-Diabetes Distress Scale

952 **6.7.3. Post-Phase 3 Questionnaires Week 8**

953 Participants randomized to escalation will sent the following questionnaires on week 8 (day 49
954 of Phase 3) and will be asked to complete them within 1 week:

- 955 • Hypoglycemia Fear Survey
- 956 • Hyperglycemia Avoidance Scale
- 957 • Confidence in Diabetes Self-Care Scale

958 **6.8. Visit 6 - Study Exit**

959 Participants will participate in a Study Exit visit either via web conference or an office visit.
960 Participants will return to their standard diabetes care using their personal equipment. The study
961 team will be available to answer questions about insulin parameters.

962 The participant will be asked to return all investigational study devices (e.g. study insulin pump,
963 study, CGM, study phone, other associated supplies) either via mail or at an office visit.
964 Participants may keep the study glucometer and ketone meter.

965 **6.8.1. Study Exit Questionnaires**

966 Participants randomized to escalation will complete the following questionnaires:

- 967 • ABACUS

CLINICAL PROTOCOL

968 • INSPiRE (revised for DSS)

969 • Diabetes Locus of Control

970 **6.8.2. Adverse Event Assessment**

971 The participant will be asked about any of adverse events, adverse device effects, and device
972 issues since the last visit. The participant will also be asked if there were any low BGs <54 mg/dL,
973 high BGs >300 mg/dL, or ketones \geq 3.0 mmol/L since the last visit.

974 **6.9. Post Study Check-In Visit (Visit 7)**

975 Approximately 48 hours after the home use of the equipment, the study team will contact the
976 participant via phone/email/text to assess:

977 • Adverse events, adverse device effects, and device issues

978 • Blood glucose values <60 mg/dL and >300 mg/dL

CLINICAL PROTOCOL

979 **Chapter 7 Study Procedures – De-Escalation**

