1122 Participants randomized to de-escalation will complete the following questionnaires:

- 1123 • ABACUS

1124 **7.8.2. Adverse Event Assessment**

1125 The participant will be asked about any of adverse events, adverse device effects, and device
1126 issues since the last visit. The participant will also be asked if there were any low BGs <54 mg/dL,
1127 high BGs >300 mg/dL, or ketones ≥ 3.0 mmol/L since the last visit.

CLINICAL PROTOCOL

1128 **7.9. Post Study Check-In Visit (Visit 7)**

1129 Approximately 48 hours after the home use of the equipment, the study team will contact the
1130 participant via phone/email/text to assess:

- 1131 • Adverse events, adverse device effects, and device issues
1132 • Blood glucose values <60 mg/dL and >300 mg/dL

1133 **Chapter 8 Testing Procedures**

1134 **8.1. Laboratory / Point of Care Testing**

1135 **8.1.1. HbA1c**

- 1136 • A blood sample will be obtained at screening to obtain a baseline hemoglobin A1c level.
- 1137 • HbA1c level may be measured by study team using the DCA2000, a comparable point of
1138 care device, at time of screening
- 1139 • Labs may be obtained at a local laboratory (e.g. LabCorp) convenient to the participant.
- 1140 • Blood test may be obtained within 14 days prior to enrollment may be used for eligibility
1141 purposes.
- 1142 • Sample collected at randomization and end of study will be used for statistical purposes.

1143 **8.1.2. Comprehensive Metabolic Panel**

- 1144 • A blood sample will be obtained at screening to assess kidney and liver functioning.
- 1145 • Labs may be obtained at a local laboratory (e.g. LabCorp) convenient to the participant.
- 1146 • Blood test may be obtained within 14 days prior to enrollment may be used for eligibility
1147 purposes.

1148 **8.1.3. Thyroid Stimulating Hormone**

- 1149 • A blood sample will be obtained at screening to assess thyroid function.
- 1150 • Labs may be obtained at a local laboratory (e.g. LabCorp) convenient to the participant.
- 1151 • Blood test may be obtained within 14 days prior to enrollment may be used for eligibility
1152 purposes.

1153 **8.1.4. Pregnancy Test**

1154 A blood/urine pregnancy test will be required for women of childbearing potential at the
1155 screening visit, and between each phase . Tests must be negative to participate in the study.

1156 **Chapter 9 Questionnaires & Ecological Momentary Analysis**

1157 **9.1. Diabetes Specific Personality Questionnaire**

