1213 This measure is used to assess the extent of potentially problematic avoidant attitudes and
1214 behaviors in people with T1DM [91]. The Hypoglycemia Avoidance Scale reliably quantifies
1215 affective and behavioral aspects of hyperglycemia avoidance and is used to assess the extent of
1216 potentially problematic avoidant attitudes and behaviors regarding hyperglycemia in people with
1217 T1DM. It has 24 items plus two additional optional items asking about the highest level of daily
1218 blood glucose or HbA1c measures the individual would feel comfortable having. Administration
1219 time is approximately 10 minutes.

CLINICAL PROTOCOL

1220 **9.9. Pittsburgh Sleep Quality Index**

1221 This questionnaire will be used to assess whether the PF and DSS improve sleep quality and
1222 quantity. The Pittsburgh Sleep Quality Index [93] is a self-report questionnaire that assesses sleep
1223 quality over a 1-month time interval. The measure consists of 19 individual items, creating 7
1224 components that produce one global score: the higher the global score, the poorer the sleep
1225 quality. Administration time is approximately 5-10 minutes.

1226 **9.10. Technology Acceptance and Expectations Survey (burdens subscale only)**

1227 The Technology Acceptance Surveys [94-95] were developed for an artificial pancreas camp study
1228 in adolescents. The 38 items in the questionnaire were based on interviews conducted with
1229 individuals who had participated in previous artificial pancreas trials about their experience
1230 regarding the device. It was subsequently adapted to assess these same measures for the PF and
1231 DSS. It assesses both positive and negative experiences with PF and DSS, including blood glucose
1232 management, device burden, and overall satisfaction. Items are rated on a 5-point scale. In this
1233 study only the burden subscale will be used. The Technology Expectations Survey has the same
1234 items included on the Technology Acceptance Survey but asks whether the individual expects to
1235 experience the various benefits and burdens from use of a device. Administration time is
1236 approximately 10 minutes.

1237 **9.11. INSPIRE (revised for DSS)**

1238 This questionnaire will be used to assess patient preferences to support effective onboarding and
1239 successful continued use of the PF and DSS. The INSPIRE survey was developed to assess various

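### Aim 2 rests on a PF-or-DSS preference that the protocol never defines, derives or analyses as a variable

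*Combined protocol and SAP*

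**What the plan says.** Aim 2, in the Protocol Summary and in section 1.2, hypothesizes that participants "will have technology intervention preferences (e.g. PF or DSS) that can be predicted by key" traits and measured behavior. It adds that these preferences foretell how well GV can be controlled with each mode. Preference is therefore both something to be predicted and something that predicts.

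The sub-aims then move to other quantities. Aim 2.1 is to "confirm that technology acceptance and trust are predictive of the level of GV control" achieved. Aim 2.2 concerns expectations and experience. Aim 2.3 is to "assess the correlation between relevant psycho-behavioral traits with the performance" of PF against DSS. Section 1.3.6 is headed "Mapping of Psycho-behavioral Characteristics to DSS Preferences and Performance", but its outcomes are glycemic performance by mode and, for each advisory module, the probability that an interaction leads to the expected action and a good glycemic result. Section 14.5 models questionnaire scores, with INSPIRE as its example, over time and against glycemic outcomes.

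The instrument closest to preference is INSPIRE (revised for DSS). Section 9.11 says of it: "This questionnaire will be used to assess patient preferences to support effective onboarding and" continued use of PF and DSS. It has 22 agree/disagree items with an N/A option. The items are not reproduced.

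**The concern.** Every completer in this crossover uses SAM, PF and DSS, so the design is well suited to finding out which mode a person would choose and whether traits explain that choice. The headline hypothesis of the personalization aim depends on such a variable.

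If the plan is followed as written, no quantity called preference exists at analysis. The team could report associations of acceptance, trust, expectations, traits or usage with GV. To answer the stated hypothesis, it would then have to pick one of these as a stand-in for preference once the data are in hand. A choice not asked for before participants leave cannot be reconstructed.

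**Working it through.** The plan states no figure on this point, so the check is mainly a reading of the schedule.

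**Step 1. Is there a preference variable?** The places where one could sit are these:
- Aims 2.1 to 2.3 (1.2) use acceptance, trust, expectations, experience, traits and performance.
- 1.3.6 uses traits and within-subject constructs as covariates, with glycemic performance and interaction probabilities as outcomes.
- 14.5 uses questionnaire scores over time and their association with glycemic outcomes.
- EMA (9.12) asks about ease of use, usefulness and trust for the program in use, one mode at a time.
- Technology Acceptance (9.10) is limited to its burden subscale.

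Count of described items that ask for a PF-versus-DSS choice: 0. Count of specified analyses with preference as outcome or predictor: 0.

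**Step 2. When is INSPIRE given?** (6.4.2, 6.6.2, 6.8.1, 7.2.2, 7.4.2, 7.6.2, 7.8.1 and the schedule in 9.13)

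| Visit | Escalation (SAM, PF, DSS) | De-escalation (DSS, PF, SAM) |
|---|---|---|
| 3 | not given | before DSS; with Technology Expectations |
| 4 | after SAM, before PF; with Technology Expectations | after DSS, before PF; with Technology Expectations and Locus of Control |
| 5 | after PF, before DSS; with Technology Expectations and Locus of Control | after PF, before SAM; with Locus of Control only |
| 6 | after DSS; with ABACUS and Locus of Control | not given (ABACUS only) |

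Each participant gets three forms.

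**Step 3. Which mode does each form rate?** The text does not say.
- *The mode just used.* Escalation Visits 5 and 6 rate PF and DSS. De-escalation Visits 4 and 5 rate DSS and PF. That is one after-use rating of each advisory mode in both sequences. The remaining form in each sequence (escalation Visit 4, de-escalation Visit 3) precedes any advisory mode and is naturally a baseline.
- *The mode about to start.* This suits the forms that sit beside Technology Expectations. It cannot apply at escalation Visit 6, where no mode follows, and at de-escalation Visit 5 a form adapted for PF and DSS would be rating SAM.

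The first reading fits the schedule better, but two of its four after-use forms are exposed. At escalation Visit 5 (after-use PF) and de-escalation Visit 4 (after-use DSS), INSPIRE is listed after training on the next mode and beside Technology Expectations. A participant could reasonably answer about the coming mode. A within-person INSPIRE difference between PF and DSS is therefore not securely interpretable as the schedule stands.

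**Step 4. What would one ranking item give?** Inputs: about 80 completers (1.5, 14.2.1) and, as an assumption, a proportion near 0.5, where precision is worst.

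Half-width = 1.96 × √(0.5 × 0.5 / 80) = 1.96 × 0.0559 = 0.11, or about 11 percentage points.

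This is the precision of the proportion ranking DSS above PF. It is not a power statement for predicting preference from traits or for relating preference to GV.

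**The case against.** The strongest reply is that the protocol already measures preference. Section 9.11 says so of INSPIRE, and INSPIRE is given three times in each sequence. Section 1.3.4 places the battery at baseline and after each modality, which supports the just-used reading. After screening, Locus of Control appears only at the same four after-PF and after-DSS visits. Technology Acceptance (burdens) is collected in week 7 of both the PF and DSS phases in both sequences, before training on the next mode, and so gives clean paired data. Section 14.5 and the mixed models in 1.3.6 use such scores. On this view only a definition is missing, in a non-primary aim, and a within-person score difference would supply it without new data.

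Much of this stands, and it rules out several stronger readings:
- A reader might infer that no participant is asked about preference. The documents do not support that: 9.11 gives INSPIRE that purpose, and its items cannot be inspected.
- A reader might infer that no schedule reading yields after-use ratings of both PF and DSS. Read as the mode just used, both sequences have them.
- A reader might treat the ABACUS-only de-escalation exit as a serious omission. That visit follows SAM, and INSPIRE has by then been given after DSS and after PF. It is weak evidence.
- A reader might infer that the trial could report only trait–GV or trait–usage associations. Sections 1.3.6 and 14.5 also allow acceptance, trust and INSPIRE scores to be related to glycemic outcomes.

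What the reply does not meet is the absence of any rule that turns these scores into a PF-versus-DSS preference, or of any analysis that uses one. Lower burden is not the same as preference, and separate ratings of single modes become a comparison only if a rule says so.

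**Conclusion.** The point holds as a definition and analysis gap in Aim 2. The hypothesis is about preference, but no comparative item is described, no preference variable is derived, and no analysis uses one. Neither predictability nor prognostic value is tested directly. The related data that are collected could support a proxy, but the proxy is not named in advance, and the INSPIRE forms that would feed it do not state which mode they rate.

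The primary outcome and Aim 1 are unaffected. The gap is worth closing because the remedy is small and the information is lost once participants exit. The 11-point half-width assumes about 80 completers who all answer and a proportion near one half. The conclusion also assumes that the undisclosed INSPIRE items contain no head-to-head choice. If they do, the missing parts are the derivation rule and the analysis.

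**What to change.** 1. At Visit 6 in both sequences (6.8.1, 7.8.1, 9.13), add one item asking the participant to rank SAM, PF and DSS by which they would choose to keep using.
2. In 1.3.6 and Chapter 14, name the DSS-versus-PF ranking as the Aim 2 preference outcome. Specify two models, both with sequence included: preference on baseline traits, and preference against the within-person DSS minus PF difference in CV. An exit ranking is collected after the CV data, so the second model should be reported as an association.
3. In 6.4.2, 6.6.2, 7.4.2 and 7.6.2, have INSPIRE at Visits 4 and 5 completed before training on the next mode. Where PF or DSS has just been used, state that the form rates that mode. Treat the form given before any advisory mode (escalation Visit 4, de-escalation Visit 3) as baseline. The within-person INSPIRE difference between PF and DSS can then be a supporting measure.

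INSPIRE need not be added to the de-escalation exit, which follows SAM.

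The cost is one question at an existing visit, a change in the order of forms already collected, and a short amendment. The downside is recency bias. DSS is the more recent of the two advisory modes in escalation and PF is in de-escalation, so including sequence in the model addresses it. If the sponsor does not want a new item, the minimum is to pre-specify the INSPIRE difference as the preference variable once item 3 is in place, or to restate Aim 2 in terms of acceptance and trust.

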1717 psychological factors (e.g., INSPIRE survey) over time, and their association with glycemic
1718 outcomes. Group assignment and Study Phases will be the primary covariate.

1719 **14.6. Baseline Descriptive Statistics**

1720 Baseline demographic and clinical characteristics of the cohort of all randomized participants will
1721 be summarized in a table using summary statistics appropriate to the distribution of each
1722 variable. Descriptive statistics will be displayed overall and by treatment group.

1723 Will include:

- 1724 • Age
- 1725 • HbA1c collected at randomization and study end
- 1726 • Gender
- 1727 • Race/ethnicity
- 1728 • CGM use before enrollment
- 1729 • Diabetes duration
- 1730 • BMI

1731 **14.7. Device Issues**

1732 We will count each time the participant interacted with the study Personalized Feedback and
1733 Decision Support System and perform a Wilcoxon paired rank test to determine if any differences
1734 exist in system interactions.

1735 **Chapter 15 Data Collection and Monitoring**

1736 **15.1. Case Report Forms and Device Data**

1737 The study data are collected through a combination of case report forms (electronic and paper)
1738 and electronic device data files obtained from the software and individual hardware
1739 components. These electronic device files and electronic CRFs are considered the primary source
1740 documentation.

1741 When data are directly collected in electronic case report forms, this will be considered the
1742 source data. Records will be maintained in accordance with ICH E6 and institutional regulatory
1743 requirements for the protection of confidentiality of participants.

1744 **15.2. Study Records Retention**

1745 Study documents will be retained for a minimum of 2 years after study close out. These
1746 documents may be retained for a longer period, however, if required by local regulations. No
1747 records will be destroyed without the consent of the Principal Investigator. It is the responsibility
1748 of the Principal Investigator to inform all co-investigators when these documents no longer need
1749 to be retained.

1750 **Chapter 16 Ethics/Protection of Human Participants**

1751 **16.1. Ethics Standard**

1752 The investigator will ensure that this study is conducted in full conformity with Regulations for
1753 the Protection of Human Participants of Research codified in 45 CFR Part 46, 21 CFR Part 50, 21
1754 CFR Part 56, and/or the ICH E6.

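### No SAM-directed expectation score exists for Aim 2.2's SAM example, and the week-7 Technology Acceptance form is concurrent with the GV outcome it would predict under Aim 2.1

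*Combined protocol and SAP*

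**What the plan says.** Section 1.2 sets two aims that link technology attitudes to glucose variability. Aim 2.1 will "confirm that technology acceptance and trust are predictive of the level of GV control" and glosses the expected negative correlation as higher "acceptance leads to lower GV". Aim 2.2 explores expectations and experience across SAM, PF and DSS. Its example is that higher expectation will "negatively correlate with GV for the SAM treatment, but not the DSS treatment".

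Section 1.3.4 announces "adapted measures for SAM and DSS technologies to capture holistic, disease-specific and" technology-specific data, and has the questionnaires completed at baseline and after each modality. Section 9.10 says of the Technology Acceptance and Expectations surveys: "It was subsequently adapted to assess these same measures for the PF and" DSS. SAM is not mentioned there.

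Section 1.3.6, tagged to Aims 2.1 and 2.2, gives an analysis rule by class of construct. Baseline traits enter as covariates. Constructs that the intervention can change are measured after each intervention and enter a mixed model. Its example of the second class is fear of hypoglycemia; acceptance and trust are placed in neither class. Section 14.5 speaks of "psychological factors (e.g., INSPIRE survey) over time, and their association with glycemic" outcomes.

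Section 1.3.1 takes GV from the last 4 weeks of each phase. The Technology Acceptance form is in the week-7 set of the PF and DSS phases (6.5.2, 6.7.2, 7.3.2, 7.5.2), sent on day 42 with one week to complete.

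**The concern.** Two gaps separate the aims from the data collected.

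First, the Aim 2.2 example contrasts SAM with DSS, but the instrument that measures expectation is never directed at SAM. In one of the two sequences it is not given at all until SAM is finished. The SAM half of the contrast could then be examined only in de-escalation, with a score about another mode, or in escalation with a score collected after the outcome.

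Second, the instrument whose name matches Aim 2.1 is completed while the outcome is being recorded. Participants may rate the system by the control they have just had. A negative correlation would fit that explanation as well as acceptance improving control. Reporting it as prediction, or as one leading to the other, would claim a time order that the data do not have.

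**Working it through.** No sample size or power figure is involved, so there is no stated figure to reproduce. The check is a count from the schedule and calendar arithmetic.

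**1. Technology Expectations against the mode that follows** (6.2.2, 6.4.2, 6.6.2, 7.2.2, 7.4.2, 7.6.2, table 9.13)

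| Visit | Escalation: next mode | Form given? | De-escalation: next mode | Form given? |
|---|---|---|---|---|
| 3 | SAM | No (sleep index only) | DSS | Yes |
| 4 | PF | Yes | PF | Yes |
| 5 | DSS | Yes | SAM | No (INSPIRE revised for DSS, Locus of Control) |

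- Forms directed at SAM: 0 + 0 = 0, hence 0 of 80 completers.
- Forms of any kind given before the SAM outcome is complete: escalation 0; de-escalation 2 (Visit 3 for DSS, Visit 4 for PF).
- The allocation ratio is not stated. If it is equal, 80 / 2 = 40 per arm: about 40 completers with no score and about 40 with two.

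**2. The week-7 form against the GV window**

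Inputs: GV window = last 28 days (1.3.1); phase length L of about 8 weeks (1.4), stated as a minimum in Chapters 6 and 7; form sent on day 42 and due by day 49. Section 6.7.2 prints day 42 of Phase 1 under a Phase 3 heading; I read it as Phase 3, as table 9.13 does.

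The window runs from day L − 27 to day L. Outcome days elapsed by the end of day d are max(0, d − (L − 28)).

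| L (days) | Window | Elapsed at day 42 | Elapsed at day 49 |
|---|---|---|---|
| 56 | 29–56 | 42 − 28 = 14 | 49 − 28 = 21 |
| 63 | 36–63 | 42 − 35 = 7 | 49 − 35 = 14 |
| 70 | 43–70 | 42 − 42 = 0 | 49 − 42 = 7 |

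A form completed on day 49 precedes the whole window only if L is at least 49 + 28 = 77 days, or 11 weeks.

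Counting only CGM recorded after the form does not solve this. At 56 days it leaves 56 − 42 = 14 days, or 56 − 49 = 7, against the 24 days that section 1.3.1 regards as optimal for CV.

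**3. Other acceptance and trust measures in the schedule**

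- INSPIRE, escalation: Visit 4 (before PF), Visit 5 (after PF, before DSS), Visit 6 (after DSS).
- INSPIRE, de-escalation: Visit 3 (before DSS), Visit 4 (after DSS, before PF), Visit 5 (after PF). Each advisory mode thus has an INSPIRE score before and after it in both arms.
- EMA ease, usefulness and trust items: last diary of each EMA day, in every phase including SAM (9.12). In weeks 1–4 this gives at most 2 fortnights × 2 to 3 days × 1 diary = 4 to 6 ratings per person per phase.

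Scores completed before the GV window therefore exist, but the plan does not assign one to Aim 2.1.

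**The case against.** The best defence is that both aims are modest. Aim 2.1 first states its hypothesis as a negative correlation, section 14.5 speaks of association, and a concurrent score can test a correlation. The causal wording is one explanatory clause. Aim 2.2 only explores, its SAM sentence is an example, and it never says that the expectation must be about SAM. All of that stands and keeps the point small. It does not supply the missing scores, and it does not make the week-7 form predictive.

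A reader might infer more than the documents support:

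- **That Aim 2.1 has no timing rule and its predictor is wholly open.** Sections 1.3.4 and 1.3.6 give timing and model by class of construct. What is missing is the assignment of acceptance and trust to a class and a score.
- **That Aim 2.2 cannot be examined under SAM at all.** If expectation means the study technology in general, de-escalation participants have DSS and PF scores before SAM. The gap is complete only in escalation.
- **That a rate of false acceptance–GV links can be calculated.** It would depend on how strongly ratings follow recent control, and the documents give no such correlation. Any percentage would mostly return the value assumed.
- **That an early EMA rating must become the predictor.** It is measured before the window, but on few ratings, and it is still confounded by underlying glucose control. Section 1.1.1 also warns that the time needed to build trust is often underestimated.

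**Conclusion.** The point holds in limited form and is worth considering; it is not a condition for the trial's main result. No participant has a SAM-directed expectation score, and escalation has no Technology Expectations score before its SAM outcome is complete, so half of the Aim 2.2 example cannot be tested as prediction in that arm. In phases of about 8 weeks the Technology Acceptance form falls inside the GV window, so it supports an association and not the predictive or causal wording of Aim 2.1. The overlap shrinks as phases lengthen beyond the 8-week minimum.

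The conclusion assumes that forms are completed within the week allowed. The per-arm counts also assume equal allocation. The primary CV comparison of SAM, PF and DSS uses none of these scores and is unaffected.

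**What to change.** 1. **Aim 2.2.** Either add the Technology Expectations form, worded for SAM, at Visit 3 in escalation and Visit 5 in de-escalation (6.2.2, 7.6.2, 9.13, with a line in 9.10), or limit the expectation example to PF and DSS. The first option costs one short form. It would be completed after participants have already used SAM in run-in, and it would be missing for cohorts past those visits. The second costs only wording, but gives up the SAM-versus-DSS contrast.

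2. **Aim 2.1 and section 1.3.6.** Replace the causal phrase with *is associated with*. State which class of construct acceptance and trust belong to. Report the week-7 Technology Acceptance result as a concurrent association. Keep *predictive* for a score completed before the GV window opens. This is wording only.

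3. **Optional sensitivity analysis.** Relate the mean EMA technology rating in weeks 1–4 of a phase to CV in its last 4 weeks, adjusted for run-in CV. The data are already collected. There are at most 4 to 6 ratings per person per phase, fewer if last diaries are skipped. Report the result as an association, because confounding by underlying glucose control remains.
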